#### Sample Size:

With a sample size of 60 subjects in the Safety and Efficacy Assessment, the study will have 79% probability of detecting AEs occurring at a rate of 5% or more in either treatment arm.

Multiplicity Consideration:

There will be no adjustments for multiple endpoints or multiple treatment comparisons for this early phase, exploratory study.

Safety Variables:

Frequencies and percentages of subjects with treatment-emergent adverse events (TEAEs), serious TEAEs, and TEAEs causing premature discontinuation will be provided by treatment group. An AE is treatment emergent if it occurs or worsens after the first dose of study treatment. Separate summaries will be provided for ocular specific and all AEs (including systemic).

Other safety endpoints including visual acuity, slit-lamp biomicroscopy, corneal sensitivity, dilated fundoscopy, intraocular pressure will be summarized by treatment group and visit using descriptive statistics. Changes or shifts from baseline will also be summarized where appropriate. For assessments performed by eye, study eye and fellow eye may be summarized separately. Summaries of the comfort data from the Comfort Assessment of the study will be performed on the safety population from that Assessment. The statistical analysis of safety data will be performed for the safety population, separately for the Comfort Assessment and the Safety and Efficacy Assessment of the study. The analysis of baseline and all efficacy data in the Safety and Efficacy Assessment of the study will be performed for the mITT population. The efficacy analyses may also be performed on the PP population as sensitivity analyses.

## 10.2 Statistical Hypotheses

For each efficacy endpoint and time point, the statistical hypotheses are as follows:

$H_0$ : There is no difference between the Naltrexone Ophthalmic Solution treatment group and placebo for the respective endpoint.

$H_1$ : There is a difference between the Naltrexone Ophthalmic Solution treatment group and placebo for the respective endpoint. A difference in favor of Naltrexone Ophthalmic Solutions will be considered a success for that endpoint.

## 10.3 Sample Size

The study is not powered to show statistical differences for any of the efficacy endpoints. The sample size was determined based on prior clinical trial experience with in subjects with dry eye syndrome and is deemed to be robust sufficient to

evaluate the safety and tolerability of Naltrexone Ophthalmic Solution in this population and to gather efficacy data that will aid in powering future clinical trials.

With a sample size of 60 subjects in the Safety and Efficacy Assessment, the study will have 79% probability of detecting AEs occurring at a rate of 5% or more in either treatment arm.

## 10.4 Statistical Analysis

### 10.4.1 General Considerations

The quantitative variables will be summarized using number of subjects (n), mean, median, standard deviation, minimum and maximum. The qualitative variables will be summarized using counts and percentages.

All summaries will be presented by treatment group.. Summaries will be provided for demographics, baseline medical history, concurrent therapies, and subject disposition.

Baseline measures are defined as the last measure prior to the initiation of study treatment, usually at Visit 2.

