#### **Visit 1 = Day -10 ± 1, Screening**

- Informed consent/Health Information Portability and Accountability Act (HIPAA) consent
- Demographic data, medical/medication, and ocular history
- Urine Pregnancy Test (if applicable)
- Ocular Surface Disease Index (OSDI)
- Ora Calibra® Ocular Discomfort Scale
- Ora Calibra® Ocular Discomfort & 4-Symptom Questionnaire
- Visual Analog Scale (VAS)
- Best Corrected Visual Acuity (BCVA)
- Slit lamp biomicroscopy
- Ora Calibra® Conjunctival redness
- Corneal sensitivity Cochet-Bonnet
- Tear film break-up time (TFBUT)
- Fluorescein staining (Ora Calibra® scale); regions: central, superior, inferior, temporal, nasal, corneal sum, conjunctival sum, and total eye score
- Lissamine green staining (Ora Calibra® scale); regions: inferior, superior, central, temporal, nasal, corneal sum, conjunctival sum, and total eye score)
- Review inclusion and exclusion criteria
- Run-in (vehicle) dose
- Dispense vehicle to all qualifying patients for BID dosing until Visit 2
- Adverse Event Query
- Schedule Visit 2

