#### **Visit 2 = Day 1, Confirmation / Baseline**

- Study Drug Collection
- Medical/medication update
- Adverse event query
- Ocular Surface Disease Index (OSDI)
- Ora Calibra® Ocular Discomfort Scale

- Ora Calibra® Ocular Discomfort & 4-Symptom Questionnaire
- VAS
- BCVA
- Slit lamp biomicroscopy
- Ora Calibra® Conjunctival redness
- Corneal Sensitivity (Cochet-Bonnet)
- Tear Osmolarity
- InflammaDry® (MMP-9) testing
- Tear film break-up time (TFBUT)
- Corneal and conjunctival fluorescein staining
- Corneal and conjunctival lissamine green staining
- Unanesthetized Schirmer's Test
- Intraocular Pressure (IOP)
- Dilated fundoscopy
- Review inclusion and exclusion criteria
- Randomize qualifying subjects
- Study treatment dose
- Dispense study drug/placebo "A" bottle for BID dosing
- Dispense dosing diary
- Adverse Event Query
- Schedule Visit 3

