#### **10.4.6 Efficacy Analyses**

The continuous and ordinal secondary efficacy variables collected at each visit will be summarized descriptively (n, mean, standard deviation, median, min and max), and analyzed with two-sample t-tests comparing each of the active treatment groups to placebo. All visit-based data will be analyzed at each visit and change from baseline. A Wilcoxon rank sum test and an ANCOVA model adjusting for baseline may be assessed where appropriate.

A full statistical analysis plan (SAP) will be finalized before database lock and unmasking.

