### ***InflammaDry®***

Levels of MMP-9 will be measured in each eye using InflammaDry at Visit 1, Visit 3 and Visit 5. The test will be recorded as either positive or negative. Sample should not be taken within two hours of any medication being instilled in either eye.

1. Open the Sterile Sample Collector (Package I)
2. Use the sampling fleece, gently dab along the palpebral conjunctiva until saturated
3. Open the Test Cassette (Package II), remove the protective cap, and insert the sampling fleece where indicated, ensuring to press down to hear the double click.
4. Place the absorbent tip in the buffer solution for at least 20 seconds.
5. Put the protective cover back over the Test Cassette and lay flat for at least 10 minutes before interpreting results.
6. Repeat test in other eye.

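### The planned efficacy comparison makes no use of the Visit 1 values that nine of the twelve efficacy measures have before randomization

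*Combined protocol and SAP*

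**What the plan says.** Section 10.4.1 defines baseline as one reading: "Baseline measures are defined as the last measure prior to the initiation of study treatment, usually at Visit 2". Section 10.4.6 sets out the comparison. Outcomes are "analyzed with two-sample t-tests comparing each of the active treatment groups to placebo", and "All visit-based data will be analyzed at each visit and change from baseline". Adjustment is optional: "A Wilcoxon rank sum test and an ANCOVA model adjusting for baseline may be assessed where appropriate". Visit 1 is not named as a covariate anywhere. Section 10.4.6 also promises a full SAP before database lock and unmasking, and no other baseline rule appears in the text supplied.

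The visit lists in Section 8.3.1 and the schedule in Appendix 1 show what is measured when. Section 6.1.1 lists twelve efficacy measures. Nine are taken at both Visit 1 and Visit 2: fluorescein staining, lissamine green staining, TFBUT, conjunctival redness, Cochet-Bonnet sensitivity, OSDI, the 0-4 discomfort scale, the 0-5 discomfort and symptom questionnaire, and VAS. By the same lists, Schirmer's test, tear osmolarity and MMP-9 start at Visit 2. For MMP-9, Appendix 2 says otherwise: "Levels of MMP-9 will be measured in each eye using InflammaDry at Visit 1, Visit 3 and Visit 5".

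Section 8.1.5 assigns the randomization number at the end of Visit 2, so every Visit 1 value precedes randomization. The only stated analytic role of these values is eligibility (Sections 5.3 and 5.4).

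**The concern.** A second pre-randomization reading, entered as a covariate, can explain between-subject variance that one reading leaves in the error term. Because it precedes randomization, it cannot bias the comparison of arms, even if mean levels move during the vehicle run-in between the two visits.

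Precision matters here despite the exploratory label. Section 10.3 says the study is not powered for efficacy but should supply data for powering later trials, and Section 10.2 counts a difference in favor of naltrexone as a success for that endpoint. With about 30 subjects per arm, the data are already being collected and paid for. Leaving them out of the comparison risks wider intervals than necessary around the estimates that later trials would rely on.

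**Working it through.** **The plan's own figure.** The only probability stated is 79% for detecting AEs at a 5% rate (Section 10.3). It reproduces with 30 per arm: 1 - 0.95^30 = 0.785. It does not involve baseline. The documents give no efficacy power, SD or between-visit correlation, so the results below rest on assumed correlations.

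**Inputs.** From the documents: 60 subjects allocated 1:1 (Section 5.2), readings at Visits 1, 2 and 5, and entry thresholds at both Visits 1 and 2 (Section 5.3 f and g). Assumed: the same SD at each visit, set to 1, and correlations r12, r15 and r25 between Visits 1, 2 and 5.

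**Variance of the quantity compared at Visit 5**

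- t-test on the Visit 5 value: 1
- t-test on change from Visit 2: 2(1 - r25)
- ANCOVA on Visit 2: 1 - r25²
- ANCOVA on Visits 1 and 2: 1 - (r15² + r25² - 2·r12·r15·r25)/(1 - r12²), which becomes 1 - 2r²/(1 + r) when all three correlations equal r

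**Equal correlations**

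| r | Change t-test | ANCOVA, Visit 2 | ANCOVA, Visits 1 and 2 | Reduction against Visit 2 ANCOVA | 60 subjects act like |
|---|---|---|---|---|---|
| 0.3 | 1.400 | 0.910 | 0.862 | 5.3% | 63.4 |
| 0.4 | 1.200 | 0.840 | 0.771 | 8.2% | 65.3 |
| 0.5 | 1.000 | 0.750 | 0.667 | 11.1% | 67.5 |
| 0.6 | 0.800 | 0.640 | 0.550 | 14.1% | 69.8 |
| 0.7 | 0.600 | 0.510 | 0.424 | 17.0% | 72.2 |
| 0.8 | 0.400 | 0.360 | 0.289 | 19.8% | 74.8 |

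**Cost of the extra covariate.** With N subjects and k covariates, the variance of the adjusted difference is inflated by about (N - 3)/(N - k - 3). For N = 60 this is 57/56 with one covariate and 57/55 with two, a ratio of 56/55 = 1.018. At r = 0.6 the net variance ratio is 0.859 × 1.018 = 0.875, so 60 subjects act like about 60/0.875 = 69.

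**Visit 1 less informative than Visit 2** (r12 = r25 = 0.5, 0.6, 0.7)

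- r15 lower by 0.1: variance ratios 0.960, 0.952, 0.953, a reduction of 4% to 5% before the cost
- r15 lower by 0.2: ratios 0.996, 0.996, 1.000
- Pure first-order autoregressive decay: ratio 1.000, since Visit 1 adds nothing once Visit 2 is known

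In the last two cases the 1.018 factor leaves a net loss of about 1% to 2%.

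**Selection at both visits.** One million subjects were simulated with equal underlying correlation, keeping those above the same threshold at both visits (-0.5, 0 or 0.3 SD). The ratios were 0.931, 0.942 and 0.949 at r = 0.5, and 0.876, 0.891 and 0.901 at r = 0.7. That is a reduction of about 5% to 12% before the cost, or 3% to 6% in standard error.

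**The case against.** The last value before treatment is an ordinary baseline rule. It falls after the run-in and immediately before randomized dosing. Nothing here is contradictory or biased, and the SAP still to come could add the covariate. This stands: the point is about efficiency only.

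Visit 1 may also be a weaker predictor than equal correlation implies. It precedes the vehicle run-in. Section 5.4 bars eye drops in general only within two hours of Visit 1 (item h) and admits users of topical products who can discontinue them (item m), so Visit 1 may reflect a different treatment state from Visits 2 to 5. This also stands. It is why the range must extend to zero and below.

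The larger gain may lie elsewhere. At r = 0.5, moving from the t-test on change to ANCOVA on Visit 2 alone takes the variance from 1.000 to 0.750, a 25% cut, against a further 11% from Visit 1. This is true, and the fix needs that step first. The two gains add together, and only the second is claimed here.

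A reader might go further and infer that all nine measures are noisy single readings. The documents do not support that. Appendix 2 averages at least two TFBUT measurements and repeats the Cochet-Bonnet step three times, and OSDI is a 12-item score with one-week recall. A reader might also infer that the staining threshold makes Visit 2 a peculiarly poor baseline. Section 5.3 applies the same threshold at Visit 1 in the same eye, so the gate affects both readings and shrinks the gain.

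**Conclusion.** The point holds as a low-cost improvement. The planned comparison makes no use of Visit 1 for nine of twelve measures. It would be too strong to say that Visit 1 never enters the efficacy analysis. Section 10.4.6 could be read to include tabulating it, and the word for usual practice in Section 10.4.1 lets it serve as baseline when Visit 2 is missing. Neither use reduces the error in the treatment comparison.

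A reader might also take a definite loss of precision as shown. It is not, because the correlations are assumptions. Against Visit 2 ANCOVA, and net of the extra degree of freedom, the change in variance is:

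- about 7% to 18% lower under equal correlations of 0.4 to 0.8 (0.918 × 1.018 = 0.935; 0.802 × 1.018 = 0.816)
- about 3% to 11% lower with selection on both visits (0.949 × 1.018 = 0.966; 0.876 × 1.018 = 0.892)
- up to about 2% higher if the Visit 1 to Visit 5 correlation decays strongly

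The selection figures apply most directly to measures with an entry threshold: fluorescein, and lissamine green or OSDI where they qualify the subject. The possible gain is modest to material, the possible loss is small, and neither case biases the comparison.

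**What to change.** In Section 10.4.6 and the SAP, for the nine measures taken at both visits, pre-specify an ANCOVA of the post-treatment value on treatment, with the Visit 1 and Visit 2 values as two separate covariates. For measures scored by eye, use the analyzed eye at both visits; for subject-level scores, use the subject's value. Section 10.4.2 takes the worst eye without saying how or at which visit it is chosen, so that rule has to be written as well.

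Keep Visit 2 as the reference for descriptive change from baseline. Do not replace it with the mean of the two visits. That would change the meaning of change from baseline, and in the case r12 = r25 = 0.7, r15 = 0.5 it raises the change-score standard error by about 4% (variance 0.600 to 0.650).

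Schirmer's test and tear osmolarity keep Visit 2 only. So does MMP-9, once the Appendix 2 timing (Visits 1, 3 and 5) is reconciled with the visit lists and Appendix 1 (Visits 2 and 5).

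The cost is a short SAP paragraph that makes ANCOVA the stated analysis for these measures instead of an option, and one degree of freedom, about 2% of variance at 60 subjects. No new data or procedures are required.

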### 10.4.2 Unit of Analysis

Safety endpoints will be analyzed for both eyes. For efficacy endpoints, the unit of analysis will be the worst eye.

### 10.4.3 Missing Data

The efficacy analyses will be performed using observed data.

### 10.4.4 Multiplicity Consideration

There will be no adjustments for multiple endpoints or multiple treatment comparisons for this early phase, exploratory study.

### 10.4.5 Safety Variables

Frequencies and percentages of subjects with treatment-emergent adverse events (TEAEs), serious TEAEs, and TEAEs causing premature discontinuation will be provided by treatment group. An AE is treatment emergent if it occurs or worsens after the first dose of study treatment. Separate summaries will be provided for ocular specific and all AEs (including systemic).

Other safety endpoints including visual acuity, slit-lamp biomicroscopy, corneal sensitivity, dilated fundoscopy, intraocular pressure will be summarized by treatment group and visit using descriptive statistics.

Changes or shifts from baseline will also be summarized where appropriate. For assessments performed by eye, study eye and fellow eye

may be summarized separately. Summaries of the comfort data from the Comfort Assessment of the study will be performed on the safety population from that Assessment. The statistical analysis of safety data will be performed for the safety population, separately for the Comfort Assessment and the Safety and Efficacy Assessment of the study. The analysis of baseline and all efficacy data in the Safety and Efficacy Assessment of the study will be performed for the mITT population. The efficacy analyses may also be performed on the PP population as sensitivity analyses.

#### **10.4.6 Efficacy Analyses**

The continuous and ordinal secondary efficacy variables collected at each visit will be summarized descriptively (n, mean, standard deviation, median, min and max), and analyzed with two-sample t-tests comparing each of the active treatment groups to placebo. All visit-based data will be analyzed at each visit and change from baseline. A Wilcoxon rank sum test and an ANCOVA model adjusting for baseline may be assessed where appropriate.

A full statistical analysis plan (SAP) will be finalized before database lock and unmasking.

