### 5.3 Inclusion Criteria

#### **Each subject must:**

- a) Be at least 18 years of age;
- b) Provide written informed consent;
- c) Have a diagnosis of type 1 or type 2 diabetes mellitus prior to Visit 1;
- d) Have a reported history of dry eye for at least 6 months prior to Visit 1;
- e) Have a history or use or desire to use eye drops for dry eye symptoms within 6 months of Visit 1;
- f) Have a corneal fluorescein staining score of  $\geq 2$  in any region (inferior, superior, or central regions) in at least one eye at Visits 1 and 2; must be the same eye at visits 1 and 2)
- g) Have at least one of the following at Visits 1 and 2:
  - i. A total lissamine green conjunctival score of  $\geq 2$  in at least one eye, based on the sum of the temporal and nasal regions at Visits 1 and 2; (must be the same eye at visits 1 and 2)
  - ii. Report an OSDI score  $\geq 20$  at Visits 1 and 2.

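### Baseline-adjusted ANCOVA should be the main efficacy analysis; section 10.4.6 leaves it optional and commits to two t-tests per endpoint and visit

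*Combined protocol and SAP*

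**What the plan says.** Section 10.4.6 of the protocol says the continuous and ordinal efficacy variables will be summarised descriptively and "analyzed with two-sample t-tests comparing each of the active treatment groups to placebo". It then adds: "All visit-based data will be analyzed at each visit and change from baseline". Each such endpoint therefore has two committed tests at each post-baseline visit, one on the visit value and one on the change.

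Baseline adjustment appears only as a possibility: "A Wilcoxon rank sum test and an ANCOVA model adjusting for baseline may be assessed where appropriate". No rule says when it would be appropriate. The section defers to a full SAP, to be finalised before database lock and unmasking, and does not bind that SAP on this point.

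Four other places bear on it:

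- Section 10.2 sets a hypothesis for each endpoint and time point and states: "A difference in favor of Naltrexone Ophthalmic Solutions will be considered a success for that endpoint". It does not say whether the visit value or the change decides.
- Section 10.4.1 defines the covariate: "Baseline measures are defined as the last measure prior to the initiation of study treatment, usually at Visit 2". Appendix 1 schedules every continuous and ordinal efficacy measure at Visit 2.
- Section 10.3 says the trial is not powered for efficacy, but one purpose of its size is "to gather efficacy data that will aid in powering future clinical trials".
- Section 10.4.3 states: "The efficacy analyses will be performed using observed data".

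**The concern.** The two committed tests sit at opposite ends of what can be done with a baseline measurement. The visit-value test ignores it. The change test subtracts it in full, which fixes the baseline slope at 1. The true slope is r × SD(follow-up)/SD(baseline), and when that is below 1 the change score over-corrects. ANCOVA estimates the slope from the data.

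This concerns efficiency and pre-specification, not validity. Averaged over randomisations, each t-test is unbiased and holds its own level. With about 30 per arm, however, chance baseline imbalances are large enough to pull the two estimates visibly apart, and the plan does not say which one is the result. At stake are the precision of the effect estimates meant to inform later trials and the meaning of success for an endpoint.

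**Working it through.** **Inputs.** About 30 per arm, 1:1 (sections 5.1 and 5.2). The one design figure in the plan confirms this: section 10.3 gives a 79% chance of seeing an adverse event with a 5% rate, and 1 − 0.95^30 = 0.785. The documents give no r, no k = SD(baseline)/SD(follow-up), and no significance level in 10.2 or 10.4.6. I assume r = 0.3, 0.5, 0.7; k = 1, 0.85, 0.7; and two-sided 5%. A k below 1 is plausible for corneal staining, because section 5.3 requires a fluorescein score of at least 2 "in any region (inferior, superior, or central regions) in at least one eye at Visits 1 and 2", which narrows the baseline range.

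**Variance of the treatment difference.** Set the follow-up SD to 1 and the variance for the visit-value test to 1. Then:

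- change: 1 + k² − 2rk
- ANCOVA: 1 − r², multiplied by 1 + 1/(60 − 4) = 57/56 = 1.018 for estimating the slope

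| k | r | Change | ANCOVA (with slope cost) | Cut vs visit value | Cut vs change |
|---|---|---|---|---|---|
| 1 | 0.3 | 1.40 | 0.926 | 7.4% | 33.8% |
| 1 | 0.5 | 1.00 | 0.763 | 23.7% | 23.7% |
| 1 | 0.7 | 0.60 | 0.519 | 48.1% | 13.5% |
| 0.85 | 0.3 | 1.2125 | 0.926 | 7.4% | 23.6% |
| 0.85 | 0.5 | 0.8725 | 0.763 | 23.7% | 12.5% |
| 0.85 | 0.7 | 0.5325 | 0.519 | 48.1% | 2.5% |
| 0.7 | 0.3 | 1.07 | 0.926 | 7.4% | 13.4% |
| 0.7 | 0.5 | 0.79 | 0.763 | 23.7% | 3.4% |
| 0.7 | 0.7 | 0.51 | 0.519 | 48.1% | −1.8% |

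In the last row the true slope is 0.7/0.7 = 1, so the change score is already optimal and ANCOVA pays only the slope cost. At k = 1, ANCOVA beats both t-tests for r between about 0.13 and 0.96. Outside that range it loses at most 1.8% to the better one.

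**In detectable-difference terms (k = 1).** With 80% power the detectable difference is (1.960 + 0.842) × √(relative variance × 2/30). For visit value / change / ANCOVA this is 0.72 / 0.86 / 0.70 SD at r = 0.3, 0.72 / 0.72 / 0.63 at r = 0.5, and 0.72 / 0.56 / 0.52 at r = 0.7.

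**Effect of chance imbalance.** One standard error of the baseline difference is √(2/30) = 0.258 baseline SD. In follow-up SD, it moves the visit-value estimate by 0.258r and the change estimate by 0.258(r − k), a separation of 0.258k. At r = 0.5 the shifts are +0.13 and −0.13 for k = 1, and +0.13 and −0.05 for k = 0.7.

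**Agreement of the two t-tests.** Simulation with bivariate normal data, 30 per arm, 40,000 trials per setting:

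| | r = 0.3 | r = 0.5 | r = 0.7 |
|---|---|---|---|
| Exactly one significant, true effect 0.5 SD, k = 1 | 31.0% | 33.0% | 40.3% |
| Same, k = 0.7 | 22.5% | 25.2% | 33.4% |
| At least one significant, no effect, k = 1 | 8.8% | 8.9% | 9.3% |
| Same, k = 0.7 | 8.1% | 8.1% | 8.4% |

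The single ANCOVA test rejected in 4.8 to 5.1% of trials with no effect.

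**One estimate.** If y = a + τg + βb + e, where g is treatment and b is baseline, then y − b = a + τg + (β − 1)b + e. The treatment term τ is the same, so ANCOVA on the visit value and on the change give the same adjusted difference.

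**The case against.** The strongest reply is that this is a preference about efficiency. The trial is exploratory, unpowered for efficacy and without multiplicity adjustment; ANCOVA is already named; and the SAP could settle the matter. All of that is true and keeps the point modest. It does not answer it: nothing in 10.4.6 obliges the SAP to choose ANCOVA, and that SAP is where the correction belongs.

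Second, the gain depends entirely on assumed r and k, and restricted eligibility tends to lower r as well as k. At k = 1 the gain over the visit-value test is only about 2% at r = 0.2, with a loss of about 1% at r = 0.1. Against whichever t-test happens to be better, the benefit can be close to nothing. This stands. But nobody knows in advance which t-test is better, the answer may differ by endpoint, and ANCOVA's loss is under 2%.

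Third, naming either t-test as the main analysis would also give one estimate and one 5% test. That is right; ANCOVA's specific addition is that visit value and change no longer give different answers. The disagreement rates also need a significance rule that the plan does not state, hence the assumed 5%.

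Fourth, section 10.4.2 uses the worst eye without saying how or when it is chosen, so the covariate is not fully defined. This affects the plan's own change score equally.

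Finally, 10.4.6 speaks of secondary variables. No efficacy endpoint is ranked primary, so that word excludes nothing.

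**Conclusion.** The concern holds. The committed analyses are valid, but in general less precise than one the plan already mentions, and they leave two competing results per endpoint and visit. Over the assumed range, the variance reduction runs from 7 to 48% against the visit-value test and from 34% down to a 2% loss against the change test. The unconditional gain is a single adjusted difference per endpoint and visit. ANCOVA does not decide which endpoint or time point is primary. The figures rest on assumed r, k and significance level and, for the simulations, on normal data and an assumed 0.5 SD effect. It should be corrected, but it does not threaten the validity of the trial.

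**What to change.** In section 10.4.6 and the SAP:

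- Make ANCOVA with treatment and the baseline (usually Visit 2) value the main analysis for each continuous or ordinal efficacy endpoint at each visit. Report the adjusted treatment difference with its 95% confidence interval.
- Keep the t-test and the Wilcoxon test as supportive.
- For measures taken by eye, state that the covariate comes from the same eye as the outcome.
- Leave MMP-9 out of this model, since Appendix 2 records it as positive or negative.

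Optionally, for endpoints measured at Visits 3, 4 and 5, add a repeated-measures model with baseline as covariate, so that subjects with partial follow-up contribute. No gain is claimed for this, because the documents give no dropout rate.

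The cost is wording, plus one model degree of freedom per analysis. No new data are needed, and the change can be made while the SAP is still open.
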